11.2.2. Belimumab Visits

- For summaries performed by belimumab visit, placebo subjects are aligned based on start of exposure to belimumab.
- Baseline for both belimumab and placebo randomized subjects will be the last non-missing value prior to or on the first treatment date, except for corticosteroid use, which is the last 7 days prior to treatment start date.
- Visits will be aligned so that each visit represents equivalent exposure time to belimumab, regardless of parent study treatment, and will be mapped accordingly based on the endpoint and scheduled visits collected.

	BEL1	13750	BEL1	12341
Belimumab	Parent Randomize	d Study Treatment	Parent Randomize	d Study Treatment
Visit Name	Belimumab	Placebo	Belimumab	Placebo
		PS Week 52/		
Year 1 Day 0	PS Week 0	OL Year 1 Week 0	Day 0	Day 364/Exit
Year 1 Week 4	PS Week 4	OL Year 1 Week 4	PS Day 28	PS Day 28 OLE
Year 1 Week 8	PS Week 8	OL Year 1 Week 8	PS Day 56	
Year 1 Week 12	PS Week 12	OL Year 1 Week 12	PS Day 84	PS Day 84 OLE
Year 1 Week 16	PS Week 16	OL Year 1 Week 16	PS Day 112	
Year 1 Week 20	PS Week 20	OL Year 1 Week 20	PS Day 140	
				PS Day 168 OLE/
Year 1 Week 24	PS Week 24	OL Year 1 Week 24	PS Day 168	OL Year 1 Week 0
Year 1 Week 28	PS Week 28	OL Year 1 Week 28	PS Day 196	OL Year 1 Week 4
Year 1 Week 32	PS Week 32	OL Year 1 Week 32	PS Day 224	OL Year 1 Week 8
Year 1 Week 36	PS Week 36	OL Year 1 Week 36	PS Day 252	OL Year 1 Week 12
Year 1 Week 40	PS Week 40	OL Year 1 Week 40	PS Day 280	OL Year 1 Week 16
Year 1 Week 44	PS Week 44	OL Year 1 Week 44	PS Day 308	OL Year 1 Week 20
	PS Week 52/OL			
Year 1 Week 48	Year 1 Week 0	OL Year 1 Week 48	PS Day 364/Exit	OL Year 1 Week 24
	is not mapped to a belim			other visits and
	t is used for any derivation			OL Vanid Wask 20
Year 2 Week 4	OL Year 1 Week 4	OL Year 2 Week 4	PS Day 28 OLE	OL Year 1 Week 28
Year 2 Week 8	OL Year 1 Week 8	OL Year 2 Week 8	DO D 04 01 E	OL Year 1 Week 32
Year 2 Week 12	OL Year 1 Week 12	OL Year 2 Week 12	PS Day 84 OLE	OL Year 1 Week 36
Year 2 Week 16	OL Year 1 Week 16	OL Year 2 Week 16		OL Year 1 Week 40
Year 2 Week 20	OL Year 1 Week 20	OL Year 2 Week 20		OL Year 1 Week 44
V 0W 104	01.77	01.1/ 01/1/ 1.04	PS Day 168 OLE/	01.7/ 4.7/ 1.40
Year 2 Week 24	OL Year 1 Week 24	OL Year 2 Week 24	OL Year 1 Week 0	OL Year 1 Week 48
Year 2 Week 28	OL Year 1 Week 28	OL Year 2 Week 28	OL Year 1 Week 4	OL Year 2 Week 4
Year 2 Week 32	OL Year 1 Week 32	OL Year 2 Week 32	OL Year 1 Week 8	OL Year 2 Week 8
Year 2 Week 36	OL Year 1 Week 36	OL Year 2 Week 36	OL Year 1 Week 12	OL Year 2 Week 12
Year 2 Week 40	OL Year 1 Week 40	OL Year 2 Week 40	OL Year 1 Week 16	OL Year 2 Week 16
Year 2 Week 44	OL Year 1 Week 44	OL Year 2 Week 44	OL Year 1 Week 20	OL Year 2 Week 20
Year 2 Week 48	OL Year 1 Week 48	OL Year 2 Week 48	OL Year 1 Week 24	OL Year 2 Week 24

Year 3 Week 4	OL Year 2 Week 4	OL Year 3 Week 4	OL Year 1 Week 28	OL Year 2 Week 28
Year 3 Week 8	OL Year 2 Week 8	OL Year 3 Week 8	OL Year 1 Week 32	OL Year 2 Week 32
Year 3 Week 12	OL Year 2 Week 12	OL Year 3 Week 12	OL Year 1 Week 36	OL Year 2 Week 36
Year 3 Week 16	OL Year 2 Week 16	OL Year 3 Week 16	OL Year 1 Week 40	OL Year 2 Week 40
Year 3 Week 20	OL Year 2 Week 20	OL Year 3 Week 20	OL Year 1 Week 44	OL Year 2 Week 44
Year 3 Week 24	OL Year 2 Week 24	OL Year 3 Week 24	OL Year 1 Week 48	OL Year 2 Week 48
Year 3 Week 28	OL Year 2 Week 28	OL Year 3 Week 28	OL Year 2 Week 4	OL Year 3 Week 4
Year 3 Week 32	OL Year 2 Week 32	OL Year 3 Week 32	OL Year 2 Week 8	OL Year 3 Week 8
Year 3 Week 36	OL Year 2 Week 36	OL Year 3 Week 36	OL Year 2 Week 12	OL Year 3 Week 12
Year 3 Week 40	OL Year 2 Week 40	OL Year 3 Week 40	OL Year 2 Week 16	OL Year 3 Week 16
Year 3 Week 44	OL Year 2 Week 44	OL Year 3 Week 44	OL Year 2 Week 20	OL Year 3 Week 20
Year 3 Week 48	OL Year 2 Week 48	OL Year 3 Week 48	OL Year 2 Week 24	OL Year 3 Week 24
Teal 5 Week 40	OL TOUTZ VVCCK 40	02 10di 0 110dik 10	OL TOUL E TYOUK ET	OL TOUR O WOOK ET
Year 4 Week 4	OL Year 3 Week 4	OL Year 4 Week 4	OL Year 2 Week 28	OL Year 3 Week 28
Year 4 Week 8	OL Year 3 Week 8	OL Year 4 Week 8	OL Year 2 Week 32	OL Year 3 Week 32
Year 4 Week 12	OL Year 3 Week 12	OL Year 4 Week 12	OL Year 2 Week 36	OL Year 3 Week 36
Year 4 Week 16	OL Year 3 Week 16	OL Year 4 Week 16	OL Year 2 Week 40	OL Year 3 Week 40
Year 4 Week 20	OL Year 3 Week 20	OL Year 4 Week 20	OL Year 2 Week 44	OL Year 3 Week 44
Year 4 Week 24	OL Year 3 Week 24	OL Year 4 Week 24	OL Year 2 Week 48	OL Year 3 Week 48
Year 4 Week 28	OL Year 3 Week 28	OL Year 4 Week 28	OL Year 3 Week 4	OL Year 4 Week 4
Year 4 Week 32	OL Year 3 Week 32	OL Year 4 Week 32	OL Year 3 Week 8	OL Year 4 Week 8
Year 4 Week 36	OL Year 3 Week 36	OL Year 4 Week 36	OL Year 3 Week 12	OL Year 4 Week 12
Year 4 Week 40	OL Year 3 Week 40	OL Year 4 Week 40	OL Year 3 Week 16	OL Year 4 Week 16
Year 4 Week 44	OL Year 3 Week 44	OL Year 4 Week 44	OL Year 3 Week 20	OL Year 4 Week 20
Year 4 Week 48	OL Year 3 Week 48	OL Year 4 Week 48	OL Year 3 Week 24	OL Year 4 Week 24
Year 5 Week 4	OL Year 4 Week 4	OL Year 5 Week 4	OL Year 3 Week 28	OL Year 4 Week 28
Year 5 Week 8	OL Year 4 Week 8	OL Year 5 Week 8	OL Year 3 Week 32	OL Year 4 Week 32
Year 5 Week 12	OL Year 4 Week 12	OL Year 5 Week 12	OL Year 3 Week 36	
Year 5 Week 16	OL Year 4 Week 16	OL Year 5 Week 16	OL Year 3 Week 40	
Year 5 Week 20	OL Year 4 Week 20	OL Year 5 Week 20	OL Year 3 Week 44	
Year 5 Week 24	OL Year 4 Week 24	OL Year 5 Week 24	OL Year 3 Week 48	
Year 5 Week 28	OL Year 4 Week 28	OL Year 5 Week 28	OL Year 4 Week 4	
Year 5 Week 32	OL Year 4 Week 32	OL Year 5 Week 32	OL Year 4 Week 8	
Year 5 Week 36	OL Year 4 Week 36	OL Year 5 Week 36	OL Year 4 Week 12	
Year 5 Week 40	OL Year 4 Week 40	OL Year 5 Week 40	OL Year 4 Week 16	
Year 5 Week 44	OL Year 4 Week 44	OL Year 5 Week 44	OL Year 4 Week 20	
Year 5 Week 48	OL Year 4 Week 48	OL Year 5 Week 48	OL Year 4 Week 24	
Year 6 Week 4	OL Year 5 Week 4	OL Year 6 Week 4		
Year 6 Week 8	OL Year 5 Week 8	OL Year 6 Week 8		
Year 6 Week 12	OL Year 5 Week 12	OL Year 6 Week 12		
Year 6 Week 16	OL Year 5 Week 16	OL Year 6 Week 16		
Year 6 Week 20	OL Year 5 Week 20	OL Year 6 Week 20		
Year 6 Week 24	OL Year 5 Week 24	OL Year 6 Week 24		
Year 6 Week 28	OL Year 5 Week 28	OL Year 6 Week 28		

Year 6 Week 32	OL Year 5 Week 32	OL Year 6 Week 32	
Year 6 Week 36	OL Year 5 Week 36	OL Year 6 Week 36	
Year 6 Week 40	OL Year 5 Week 40	OL Year 6 Week 40	
Year 6 Week 44	OL Year 5 Week 44	OL Year 6 Week 44	
Year 6 Week 48	OL Year 5 Week 48	OL Year 6 Week 48	
Year 7 Week 4	OL Year 6 Week 4	OL Year 7 Week 4	
Year 7 Week 8	OL Year 6 Week 8		
Year 7 Week 12	OL Year 6 Week 12		
Year 7 Week 16	OL Year 6 Week 16		
Year 7 Week 20	OL Year 6 Week 20		
Year 7 Week 24	OL Year 6 Week 24		
Year 7 Week 28	OL Year 6 Week 28		
Year 7 Week 32	OL Year 6 Week 32		
Year 7 Week 36	OL Year 6 Week 36		
Year 7 Week 40	OL Year 6 Week 40		
Year 7 Week 44	OL Year 6 Week 44		
Year 7 Week 48	OL Year 6 Week 48		
Year 8 Week 4	OL Year 7 Week 4		

PS = Parent Study, OLE = Open-label extension of BEL112341, OL = Open-label study BEL114333

11.3. Appendix 3: Adverse Event Collapsing Rules and Assignment of Adverse Events to Study Year

11.3.1. Adverse Event Collapsing

- Adverse events were collected in both the parent studies and study BEL114333.
- Due to the ongoing nature of some AEs at the end of the parent study, some AEs originate in the parent study and continue into the BEL114333 study; however, such events will be counted once only.
- The following table shows where AEs reside by their relationship to the parent study exit date or Year 1 Day 0 visit of the BEL114333 study.

AE Occurrence	Database
AE starts and ends on/before parent study Exit Visit.	Parent study only.
AE starts on/before Exit Visit in the parent study and ends either on/after Year 1 Day 0 of BEL114333, or after the Exit Visit but before Year 1 Day 0 of BEL114333 (where there is a gap between these visits). ¹	Parent study and BEL114333 ²
AE starts after Exit Visit of the parent study and ends before Year 1 Day 0 of the BEL114333 study (where there is a gap between these visits).	BEL114333 only
AE starts after Exit Visit of the parent study and ends on/after Year 1 Day 0 of the BEL114333 study (where there is a gap between these visits).	BEL114333 only
AE starts and ends on/after Year 1 Day 0 of the BEL114333 study.	BEL114333 only

¹ Records to be collapsed.

- AEs that occur in both the parent study and study BEL114333 will be collapsed based on the following dataset attributes: MedDRA lower level term, AE start date, and action taken with Investigational Product (IP).
 - AEs in both the parent study and BEL114333 should be considered one event if they match on the attributes noted above. Severity, Seriousness and Relationship to IP should reflect worst case between the two collapsed records. Outcome and end date should reflect the final outcome in BEL114333.

²Ongoing AEs in the parent study BEL112341 were entered by site in the BEL114333 eCRF. Ongoing AEs in the parent study BEL113750 were programmatically added to the BEL114333 data transfer.

Values from BEL112341 may be mapped as appropriate. Note: AE Start Time
was collected in BEL114333 but not in BEL112341, so the date part will be used
for AE collapsing.

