4.4. Withdrawal Criteria

A subject may voluntarily discontinue participation in this study at any time. The investigator may also, at his or her discretion, discontinue a subject from this study. Every effort should be made by the investigator to keep subjects in the study and to ensure return for the Exit visit 4 weeks after the last dose of belimumab, and the follow-up visits 16 weeks after the last dose. For any subject who had an anti-belimumab antibody response at the 16-week follow-up visit (or last study visit at which immunogenicity was assessed if the 16-week follow-up immunogenicity sample is not available), an attempt will be made to obtain a serum sample for anti-belimumab antibodies at least 6 months after the last dose of study agent. From subjects at selected sites only, B-cell subsets will be collected at the EXIT visit and at approximately 6 months after the last dose of study agent.

Notwithstanding this requirement, the investigator should adjust concurrent medications as clinically required.

Reasons for subject withdrawal include “adverse event”, “lack of efficacy”, “protocol deviation”, “study closed/terminated”, “lost to follow-up”, “investigator discretion”, and “withdrew consent”. The investigator will record the primary reason in the electronic case report form (eCRF) and any data collected up until the point of withdrawal, and the follow-up visits will be used in the analyses.

If a subject is permanently discontinued from belimumab during the course of the study, the subject must be withdrawn from the study. In addition, subjects will be withdrawn from the study if any of the following criteria are met:

- **Unacceptable toxicity** including:
 - **Laboratory parameters:** Demonstrate clinically important changes in laboratory parameters.
 - **Liver Chemistry:** Detailed in Section 6.3.1.
- **Pregnancy:** Positive urine pregnancy test.
- **Concurrent Medication:** Prohibited concurrent medication or therapy (See Section 5.3.2 and Section 5.3.3).
- **Consent:** Withdrawal of consent.
- **Compliance:** Missed 3 or more consecutive study infusions.

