Subjects should be made aware of the potential risk, the signs and symptoms of such reactions, and the importance of immediately seeking medical attention. Trained rescue personnel and rescue medications/equipment should be available for a minimum of the first 2 doses. For subjects who have previously received intravenous immunoglobulins (IVIG) or subjects with a history of allergies (allergic responses to food, drugs, insects, or a history of urticaria), administering premedication for prophylaxis against infusion reactions and hypersensitivity reactions should be considered. If a subject experiences a clinically significant AE that, in the clinical judgement of the investigator, is possibly, probably or definitely related to belimumab, and this AE continues at the next scheduled dose, or could potentially be exacerbated by the next dose, the investigator may delay the dose by up to 2 weeks or withhold 1 dose. If a similar concern is present at the time of the next scheduled dose, the investigator should contact the Medical Monitor to determine whether treatment with belimumab should be discontinued.

If a subject experiences a clinically significant, potentially life-threatening (Grade 4) AE that in the clinical judgement of the investigator is possibly, probably or definitely related

to belimumab then treatment with belimumab will be discontinued. The subject should be withdrawn from the study and followed at regularly scheduled monthly study visits as required until resolution of the AE(s) and must also return for follow-up at the EXIT visit 4 weeks after the last dose of belimumab, and the follow-up visit 16 weeks after the last dose. For any subject who had an anti-belimumab antibody response at the 16-week follow-up visit (or last study visit at which immunogenicity was assessed if the 16-week follow-up immunogenicity sample is not available), an attempt will be made to obtain a serum sample for anti-belimumab antibodies at least 6 months after the last dose of study agent. From subjects at selected sites only, B-cell subsets will be collected at the EXIT visit and at approximately 6 months after the last dose of study agent.

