7.2.1. Adverse Events

• Data from all subjects as one belimumab group will be summarised.

- All adverse event tables will show the data by year interval at the start of an AE, and include a summary over the total post-baseline period. Year interval is defined in Appendix 2: Assessment Windows.
- Any AEs that started prior to the first IP administration in the parent study will not be reported. See Section 6.2, footnote 4 in Table 4 for relevance for such AEs as past medical history terms. Only treatment-emergent adverse events will be summarised.
 - o Treatment-emergent AEs are defined as follows:
 - AEs that started on or after the first dose of belimumab treatment.
 - For those subjects who were randomised to placebo in the parent study, ongoing AEs that started before the first open-label belimumab dose (in either BEL112341 open-label extension or BEL114333) and worsened (severity, seriousness, relatedness) at any point during the open-label treatment.
 - Ongoing AEs that started before the first open-label belimumab dose which
 did not worsen during the open-label treatment (for those subjects who were
 randomised to placebo during the parent study) will not be considered
 treatment-emergent, but will be listed.
- Listings will be generated by the parent randomized treatment group (see Table 8). All treatment-emergent AEs as defined above will be listed plus any ongoing AEs that started before the first belimumab dose (for subjects randomised to placebo in the parent study) that were not considered treatment-emergent. AEs that started in each parent study will be flagged.
- The hierarchical relationship between MedDRA SOCs, PTs and verbatim text will be displayed as a listing for all AEs.
- Adverse events in BEL114333 will be coded to the current MedDRA dictionary version at the time of study reporting (version 22.0).
 - NOTE: the same version of the MedDRA dictionary which was used at the time of reporting the parent studies will be used for this current reporting (BEL113750, version 21.1; BEL112341, version 18.0). Any major coding discrepancies between different versions of MedDRA can be addressed in a CSR appendix, if necessary.

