11.3.2. Assigning Adverse Events to Study Year

The following rules will be used for allocating AEs to study year:

- Each AE will be reported in the year it started.
- AEs continuing for more than one treatment year will only be reported in the year they first occurred.
- If distinct episodes (start and stop date) of an AE are reported in multiple years, the AE will be reported once in each study year in which the unique event began.
- AEs with partial start and/stop dates will be assumed to have occurred on treatment unless there is evidence through comparison of partial dates to suggest otherwise.
- Where possible the non-missing information will be used to assign the AE to a study year, if the non-missing information is insufficient to assign the AE to a study year then the AE will be assigned to the earliest plausible study year.
- If the AE onset date is missing assume the start date was in Year 0-1. The event will be reported in Year 1 and "Any Time Post-Baseline."
- If the AE end date is missing assume the AE continued until the end of study. The AE will be reported in year of onset and "Any Time Post-Baseline."
- AEs that begin and end on the first day of treatment will count in the Year 0-1 period and for "Any Time Post-Baseline."

Table 15 Example of Assigning AEs to Study Years

Scenari o	Pre-Treatment	Year 0-1	Year 1-2	Year 2-3	Year 3-4	Year 4-5	After End of Treatment
Α	←						
В		←					
С		4					———
D	←		+				

NOTE: Arrow indicates the start and stop date of a single AE.

Scenari	Assignment of AE to Study Year Any Time Post-Baseline Year 0-1 Year 1-2 Year 2-3 Year 3-4 Year 4-									
0										
Α	No	No	No	No	No	No				
В	Yes	Yes	No	No	No	No				
С	Yes	Yes	No	No	No	No				
D	Yes	No	Yes	No	No	No				

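### SAP 11.3.1 counts a carried-over AE once, but merges its two records only if action taken also matches; a changed action adds one false event to one early year column and to Any Time Post-Baseline

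*SAP*

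**What the plan says.** SAP 11.3.1 states the counting principle: "some AEs originate in the parent study and continue into the BEL114333 study; however, such events will be counted once only". Its table marks, as records to be merged, every AE that starts on or before the parent Exit visit and ends after it. The operative rule is narrower: "AEs in both the parent study and BEL114333 should be considered one event if they match on the attributes noted above". Those attributes are "MedDRA lower level term, AE start date, and action taken with Investigational Product (IP".

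Once two records are merged, "Severity, Seriousness and Relationship to IP should reflect worst case between the two collapsed records", and outcome and end date come from BEL114333. Action taken is not among the reconciled fields, and no other rule merges a pair that fails the match.

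Three further rules decide what an unmerged pair does:

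- SAP 7.2.1 defines as treatment-emergent "AEs that started on or after the first dose of belimumab treatment".
- SAP 11.3.2 assigns the year by onset: "Each AE will be reported in the year it started".
- SAP 7.2.2 calculates rates as 100 times the number of events divided by subject-years.

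**The concern.** Severity, seriousness, relationship, outcome and end date can all change while an AE continues, so the SAP lets them differ and reconciles them. Action taken can change in the same way but is used as an identifier.

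The protocol gives two ordinary routes to a change after rollover. For a clinically significant, related AE that continues at the next dose or could be made worse by it, "the investigator may delay the dose by up to 2 weeks or withhold 1 dose" (Section 5). Under Section 4.4, "If a subject is permanently discontinued from belimumab during the course of the study, the subject must be withdrawn from the study". Entrants have completed the parent study or its extension, so a carried-over AE that first leads to discontinuation in BEL114333 would be expected to show a different action in its parent record. The key therefore tends to fail for AEs that had consequences for dosing.

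At stake are event counts and rates. Person-year-adjusted AE rates are among the primary safety endpoints in SAP 2.2, and Tables 2.30 and 2.31 report occurrences as well as subjects. In an unmerged pair, the parent record also keeps its old severity and outcome.

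**Working it through.** The plan gives no figure to reproduce. The check applies its rules to a pair of records from one subject with the same lower level term and the same start date.

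**1. Events counted per pair**

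- Same action in both records: 1 event in the onset year and 1 in Any Time.
- Changed action, BEL113750 belimumab arm, onset Day 300: Year 0-1 = 2, Any Time = 2.
- Changed action, BEL112341 placebo arm, onset Day 100 of open-label belimumab: Year 0-1 = 2, Any Time = 2.
- Changed action, BEL112341 belimumab arm, onset Day 450: Year 1-2 = 2, Any Time = 2.
- Action taken removed from the key: 1 and 1 in every case.

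An AE that began before the first belimumab dose and did not worsen is not treatment-emergent, so it adds nothing under either key.

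**2. Which year columns a pair can reach**

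Under SAP 11.2.1 the first belimumab dose is Day 1, so analysis day = protocol day + 1. Year 0-1 is Days 1-365 and Year 1-2 is Days 366-730. The latest parent-study onsets on belimumab are:

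- BEL113750, belimumab arm: the nominal Week 52 visit is 364 + 1 = Day 365, or Day 372 with the +7 day window. The Week 52 visit serves as Day 0, and Day 0 may fall up to 8 weeks after the last parent dose. If that dose is at Week 48 (336 + 1 = Day 337), the limit is 337 + 56 = Day 393, or Day 400 if Week 48 is itself 7 days late. This assumes that the Week 52 visit moves with Day 0. If it does not, AEs starting in the gap sit in BEL114333 alone and cannot be duplicated.
- BEL112341, belimumab arm: 364 + 168 + 1 = Day 533, about Day 540 with a 7-day window.
- BEL112341, placebo arm: belimumab starts at Day 0 of the extension, so 168 + 1 = Day 169, or Day 176 with the window.

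All of these fall before Day 731, so no pair reaches Year 2-3. In the BEL112341 belimumab arm, Days 366-533 fall in Year 1-2: 533 − 366 + 1 = 168 days, and 168/533 = 31.5% of the nominal onset window. That is a share of days, not of events.

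**3. Effect of one pair on a rate**

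With E true events and PY person-years, 100(E + 1)/PY − 100E/PY = 100/PY. The documents give no person-years. For illustration only, if a column held 75 to 150 person-years, one pair would add 100/75 = 1.33 to 100/150 = 0.67 events per 100 person-years.

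**4. Subject counts**

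Both records belong to one subject, who is counted once. The number (%) with a given AE does not change.

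**The case against.** Several features narrow the exposure.

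- Ongoing BEL113750 AEs were added to the BEL114333 transfer by program, and SAP 5.1 says one database captures both studies and sites could still edit parent data. If the second record is a copy, the actions agree unless the two were edited separately. The protocol requires transferred AEs to be followed up in BEL114333, but neither document says which record is updated. This stands: BEL113750 exposure is possible but not shown.
- For BEL112341, SAP 11.3.1 permits values to be mapped where appropriate. That may align codes between studies. It does not say what happens when the action really changed.
- Exclusion criterion 1 (Protocol 4.3) keeps out subjects with uncontrolled non-SLE disease or a parent-study AE posing undue risk, and the delay-or-withhold provision covers only related, clinically significant AEs. Both make mismatches rarer.
- Adjudication of AEs of special interest treats a malignancy flagged more than once as one event (SAP Appendix 10). Ordinary AEs have no such safeguard.

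A reader might infer that one pair inflates both Year 0-1 and Year 1-2. It cannot, because the two records share a start date. A reader might also infer that subject percentages are inflated, or that a decline in rates over the years is an artefact. The first does not follow, and the second would need several pairs, which nothing in the documents shows.

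**Conclusion.** The contradiction is real. Followed as written, the merge rule defeats the section's own count-once principle whenever action taken changes for an AE that began on belimumab. Each unmerged pair adds one false event, with no person-years, to one of Year 0-1 or Year 1-2 and to Any Time Post-Baseline. Year 2-3 onward and subject counts are untouched, so the two earliest year columns could be counted on a different basis from the later ones.

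The number of pairs is not derivable and is probably small, and no hypothesis is tested. The conclusion assumes only that some AE ongoing at rollover later had a different recorded action. The BEL112341 randomised split among the 25 subjects is not given, so the number who could contribute to Year 1-2 is unknown. The correction is worth making because it is cheap and touches a primary safety endpoint, not because a large bias is expected.

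**What to change.** In SAP 11.3.1:

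- Drop action taken from the key and match on subject, lower level term and start date. Episodes with different start dates stay separate.
- Carry the most consequential action taken to the merged record, using a stated order of the eCRF action categories. The SAP has no such order, so it must be written down. Without this step, an AE that led to discontinuation could drop out of the discontinuation tables.
- Before database freeze, list parent/BEL114333 pairs with the same subject and start date that remain unmatched, and resolve them by review, starting with the 25 BEL112341 subjects. The same listing would show lower level term mismatches, which are possible because SAP 7.2.1 uses MedDRA 18.0, 21.1 and 22.0 across the three studies.

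The cost is minor programming, one review listing and a footnote that the action shown for a merged AE may differ from the parent-study listing. No new data are needed.
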